⁹ Observe the subject as he/she administers the first dose of study medication while in the clinic at Visit 2. One bottle of study medication and applesauce will be distributed at this visit. For all subjects, the last dose of treatment will be administered the evening before Visit 3;

¹⁰ Subjects should return the bottle of study medication to the site at Visit 3 for drug accountability. If the study medication is not returned, the bottle should be returned to the site at the subsequent office visit (Visit 4);

¹¹ A follow-up clinic visit will occur approximately 7 days after the last clinic visit to review any on-going or evaluate newly occurring adverse events (AEs), to record any changes in concomitant medications, to assess the subject's condition via physical examination, and to obtain laboratory samples. This will conclude the subject's involvement in the study.

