5.5 Supply and Dosing

Treatments will be blinded and double-dummy, whereby subjects will be randomized to either lubiprostone sprinkle, lubiprostone capsule, or matching placebo doses BID. Each treatment day should consist of two (2) doses of study medication, one dose in the morning and one dose in the evening with meals. The Sprinkle formulation is supplied in an easy-to-open hard capsule and will be sprinkled onto a teaspoon of applesauce for oral administration, followed by intake of 240 mL of water. The Capsule formulation will also be taken with 240 mL of water.

All doses should be taken at least 5 hours apart. The subject should record the actual time the dose was taken in the electronic diary. If taken late, the site personnel should record the actual time the dose was taken in the subject records. If the dose was missed entirely, the subject should indicate the omission in the electronic diary as instructed. The study medication will be handled by authorized personnel and dispensed under the supervision of the Investigator or designated study personnel.

Subjects should return the used bottles of study medication at Visit 3 for collection by site for drug accountability. If the study medication is not returned, all bottles of unused study medication should be returned to the site at the subsequent office visit (Visit 4). The last dose of study medication in this study will be taken the evening before Visit 3.

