6.1.2.2 Randomization Visit – Visit 2 (Day 1)

The treatment period will begin at randomization when the first dose of study medication is administered on the morning of Study Day 1 and will continue with BID dosing thereafter through administration of the last dose on the evening of Day 7.

On Day 1, the following procedures will be performed:

- Review the diary record to confirm that the subject meets the necessary inclusion criteria;
- Update medical history. Any new medical information should be added to the subject's baseline history (AEs will be captured on the AE page);
- Collect blood and urine samples for laboratory analysis;
- Review and record any new AEs and follow-up on any ongoing AEs;
- Measure weight;

- Update Concomitant Therapy – Concomitant medications (prescribed and OTC) used since the Screening Visit will be reviewed;
- Measure vital signs (body temperature, respiration rate, and orthostatic blood pressure and heart rate [i.e., first measurement after 5 minutes in supine position, followed by a second measurement after 5 minutes in standing position]) at 0 hour (pre-dose) and at 1 hour post-dose. If abnormalities in blood pressure (i.e., systolic pressure <90 mmHg and/or diastolic pressure <60 mmHg, or a decrease in orthostatic systolic and/or diastolic pressure [from supine to standing] of ≥20 mmHg) are observed at 1-hour post-dose, a repeat measurement of orthostatic blood pressure and heart rate must be taken at 2 hours post-dose. If abnormalities persist at 2 hours post-dose, subject should be discontinued immediately, and an AE of hypotension should be recorded;
- Dispense study medication, providing dosing instructions (see [Section 5.5](#)) and remind the subject to bring the bottle back at the next visit;
- Observe the subject as he/she administers the first dose of study medication while in the clinic and record time of study medication administration in the electronic diary.
- If the subject is randomized, the diary must be switched to “treatment period” mode and the subject must continue completing the diary each day during the treatment period. Diary data will be automatically transmitted from the device each night. The diary will record information for the entire period prior to the next scheduled office visit;
- Remind the subject that rescue medication is prohibited during the treatment period; and
- Schedule the next clinic visit (Visit 3).

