6.1.4 Follow-up Period

The Follow-up period lasts until Day 15 (+3 days). AEs should be followed to assess their status and resolution during this timeframe. Any new concomitant medications should also be recorded.

At this visit the following procedures will be performed:

- Measure vital signs, including weight. Subjects should be asked to remain supine for at least 5 minutes prior to measurement of vital sign parameters;
- Perform an abbreviated physical examination;
- Collect blood and urine samples for laboratory analysis;
- Review and update concomitant therapy; and
- Review and record any new AEs.

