6.3 Safety Evaluations

The following safety evaluations will be performed during the study to measure the safety of the study medication:

Adverse Events: AEs will be reported by the subject from the time of informed consent through the end of the follow-up period. AEs will be followed by the Investigator as determined by Sponsor or designee. Further details on AE reporting are provided in [Section 7](#).

Clinical Laboratory Tests: The following laboratory tests will be conducted and the appropriate Investigator shall determine the clinical significance of any out-of-range values.

- **Hematology Panel:** Hemoglobin, hematocrit, MCV, MCH, MCHC, RBC, WBC, white blood cell with absolute counts and percent differentials (neutrophils, lymphocytes, monocytes, eosinophils, basophils), and platelet count.
- **Chemistry Panel:** Total cholesterol, triglycerides, glucose, total protein, albumin, alkaline phosphatase, AST, ALT, GGT, iron, LDH, total bilirubin, direct bilirubin, BUN, uric acid, creatinine, sodium, potassium chloride, bicarbonate, calcium, phosphorus, and magnesium.
- **Urinalysis:** Protein, glucose, ketones, occult blood, pH, specific gravity, color, appearance, leukocyte esterase nitrite, bilirubin, and macroscopic examination. Microscopic examination will be done if abnormalities are present. Urine samples will be collected, when possible from all subjects.

Physical Examination: Physical examinations will be conducted at various time points during the study. Any new post-treatment findings or changes, as noted by the Investigator, will be reported as an AE.

Vital Signs: Vital signs (including height and weight at designated visits) will be recorded during the study. Any post treatment clinically significant changes in vital signs shall be noted by the Investigator and reported as an AE. For example, if abnormalities in orthostatic blood pressure measurements (i.e., systolic pressure <90 mmHg and/or diastolic pressure <60 mmHg, or a decrease in orthostatic systolic and/or diastolic pressure [from supine to standing] of ≥20 mmHg) are observed at 1-hour post-dose on the day of first dose (Randomization), a repeat measurement of orthostatic blood pressure and heart rate must be taken at 2 hours post-dose. If such abnormalities persist at 2 hours post-dose, subject should be discontinued immediately, and an AE of hypotension should be recorded.

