7. ADVERSE AND SERIOUS ADVERSE EVENTS

As defined in ICH GCP Guideline E6,⁷ an AE is any untoward medical occurrence in a clinical investigation subject administered a pharmaceutical product and which does not necessarily have a causal relationship with this treatment. An AE can therefore be any unfavorable and unintended sign (including an abnormal laboratory finding), symptom, disease or exacerbation of a pre-existing condition temporally associated with the use of a medicinal (investigational) product, whether or not related to the medicinal product. For this study, all safety information will be collected from the time of informed consent and any untoward medical occurrence after screening will be defined as an AE. Adverse events that are reported after initiation of study medication, and on or before the last day of study medication plus 7 days, will be defined as treatment-emergent AEs.

Each AE requires a complete and thorough description including date of onset, duration, intensity/severity, its relationship to the study drug and any corrective actions taken. Each AE should also be categorized as “serious” or “non-serious”.

Timely, accurate, and complete reporting and analysis of safety information from the clinical study are crucial for the protection of subjects and are mandated by regulatory agencies worldwide.

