8.6.2 Adverse Events

The original terms used in the eCRF by Investigators to identify AEs will be coded to MedDRA® system organ class and preferred terms. Adverse events will be summarized in terms of incidence per dose group and overall. The incidence of an AE is defined as the number of subjects who experienced at least one episode during the study. Adverse event incidence rates will be summarized by system organ class (SOC) and preferred term (as determined by the coding).

Whatever the level of classification, if a subject experiences multiple episodes of an event within the given time reference, then the event is only counted once. Further, for summaries by severity or causality, the most severe event is chosen for a subject if that subject experiences multiple episodes of the same event

AEs with onset dates between consent and prior to administration of the first dose of study medication or after the last day of treatment + 7 days will be considered non-treatment emergent, and excluded from the tabulations. Events with completely or partially missing onset dates will be included in the tabulations unless the available partial date information clearly indicates that the event happened outside of the treatment period.

P-values from Fisher's exact test or chi-square test will be presented in the AE summary tables. The test will be performed to compare incidence rates between the sprinkle and capsule formulations of lubiprostone and the matching placebo group.

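### The AE tables stop at Day 14, one day before the earliest scheduled follow-up visit, and sections 7 and 8.6.2 define treatment-emergent AEs by different dates

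*Combined protocol and SAP*

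**What the plan says.** AE incidence is the first safety endpoint in section 2.2.2. Section 8.6.2 defines incidence as "the number of subjects who experienced at least one episode during the study". The same section then limits what is tabulated: AEs with onset before the first dose, or "after the last day of treatment + 7 days will be considered non-treatment emergent, and excluded from the tabulations". Events with missing or partial onset dates are kept unless the partial date clearly places them outside the treatment period.

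Section 7 defines treatment-emergent AEs differently: "Adverse events that are reported after initiation of study medication, and on or before the last day of study medication plus 7 days". The number of days is the same, but the clock runs on the reporting date. Section 7.1.5 has both the reporting date and the start date recorded.

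On timing, section 6.1.2.2 has dosing continue "through administration of the last dose on the evening of Day 7". Section 5.5 puts it another way: "The last dose of study medication in this study will be taken the evening before Visit 3". Visit 3 is Day 8 (+2 days) and Visit 4 is Day 15 (+3 days). Visit 4 takes blood and urine, vital signs and an abbreviated examination (section 6.1.4). Footnote 11 to the Schedule of Evaluations lists, first among its purposes, "to review any on-going or evaluate newly occurring adverse events (AEs". For examination findings, section 6.3 says: "Any new post-treatment findings or changes, as noted by the Investigator, will be reported as an AE".

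**The concern.** Visit 4 is the last planned chance to detect a new AE, and the plan spends a blood draw, a urine sample and an examination on it. If the tabulation limit falls before the visit takes place, an AE whose onset is that visit's finding is recorded on the eCRF and then left out of the AE tables. The safety endpoint would then take new laboratory or examination AEs from Visit 3 but not, in the ordinary case, from Visit 4.

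The second problem does not depend on how onset is dated. Two sections give two rules for the same term. A programmer following section 7 and one following 8.6.2 could classify the same event in opposite ways and produce different incidence counts for a named endpoint.

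**Working it through.** The plan states no figure to reproduce; the check is day counting.

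**Inputs**
- Last dose, completer: Day 7 (section 6.1.2.2).
- Tabulation limit: onset no later than last treatment day + 7 (section 8.6.2).
- Treatment-emergent limit: reported no later than last medication day + 7 (section 7).
- Visit 3: Day 8, 9 or 10. Visit 4: Day 15, 16, 17 or 18 (section 3.1).

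**Step 1. Limit against visit window.** Limit = 7 + 7 = Day 14. Visit 4 exceeds it by 15 − 14 = 1 day to 18 − 14 = 4 days. Permitted Visit 4 days inside the limit: 0 of 4.

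**Step 2. The section 5.5 wording.** If dosing runs to the evening before a late Visit 3, the limit moves:

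| Visit 3 | Last dose | Limit (last dose + 7) | Permitted Visit 4 days inside |
|---|---|---|---|
| Day 8 | Day 7 | Day 14 | none |
| Day 9 | Day 8 | Day 15 | 15 |
| Day 10 | Day 9 | Day 16 | 15, 16 |

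A Visit 4 held exactly 7 days after Visit 3 is at last dose + 8 in every row, one day outside. But footnote 11 asks only for about 7 days, and section 6.1.1 times visits from the first dose. Some Visit 4 days inside the limit are therefore possible under this reading.

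For early stoppers (last dose Day 1 to 6) the limit is Day 8 to 13. If their Visit 4 is kept on Day 15 to 18, it is outside.

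**Step 3. Which AEs are excluded.** Section 8.6.2 works on onset, not detection. An AE found at Visit 4 but dated to Day 14 or earlier stays in the tables, as does one with a missing onset date. The AEs lost are those with onset dated after the limit. For an asymptomatic finding, this assumes that onset is dated to the day of the sample or examination; the documents do not say how it is dated.

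**Step 4. The two definitions.** Take onset on Day 9, first reported at Visit 4 on Day 15, last dose Day 7.
- Section 8.6.2: 9 ≤ 14, treatment-emergent.
- Section 7: 15 > 14, not treatment-emergent.

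The same holds for any AE that starts after Visit 3, up to Day 14, and is first reported at Visit 4. With the last dose on Day 7, that span is 14 − 8 = 6 days if Visit 3 is on Day 8, and 14 − 10 = 4 days if it is on Day 10.

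**Step 5. Window that would reach the visit.** Day 15 needs 15 − 7 = 8 days after the last dose. Day 18 needs 18 − 7 = 11 days.

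**The case against.** A prespecified 7-day off-drug window after 7 days of dosing is a legitimate choice, and nothing in the documents shows that 11 days is pharmacologically better. That stands. The point is only that the window misses the visit scheduled to look for new AEs.

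The study-wide wording of the incidence definition is also not, by itself, a contradiction. The same section qualifies it by a time reference and states the exclusion openly. On the two definitions, only 8.6.2 says what leaves the tables, so a programmer who keeps to section 8.6 would retain the Day 9 example. That makes the conflict a risk to be removed, not a demonstrated error in a table.

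A reader might infer that a liver-test rise first seen at Visit 4 disappears from the report. The documents do not support that:
- Section 8.6.3 carries it in the mean changes. As both the maximum and the final value, it also enters two of the cross-tabulations, though without grading.
- Deaths, SAEs and discontinuations due to AEs are listed under 8.6.1 with no date limit.
- Hepatotoxicity must be reported to the sponsor within 24 hours whatever its seriousness (section 7.2.1).
- Clinically significant laboratory values are flagged on the eCRF (section 8.8), and the synopsis promises a summary of clinical abnormalities.

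Sections 8.6.4 and 8.6.5 likewise keep Visit 4 examinations and vital signs in view. Laboratory grading and a listing of special-interest events are details that the SAP mentioned in section 8 may supply, so their absence from the protocol section is not part of this point.

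A reader might also infer that every AE discovered at Visit 4 is excluded, or that no Visit 4 day can ever fall inside the limit. Steps 2 and 3 show that neither is so.

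**Conclusion.** The point holds, and it is minor. For a completer who stops on Day 7, all 4 permitted follow-up days lie 1 to 4 days beyond the tabulation limit. A non-serious AE whose onset is dated to that visit is collected but left out of AE incidence. The loss is in tabulation, not in collection or expedited reporting. It rests on dosing ending on Day 7 and, for asymptomatic findings, on onset being dated to the visit. A late Visit 3 with dosing up to the evening before moves the limit to Day 15 or 16 and partly closes the gap.

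The conflict between sections 7 and 8.6.2 needs only a last dose on Day 7 and an AE that starts in the 4 to 6 days between Visit 3 and Day 14 and is first reported at Visit 4.

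How many subjects either problem would touch cannot be estimated from the documents. They describe no liver signal, and the equivalence conclusion does not depend on this point.

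**What to change.** Before unblinding, put one onset-based definition in both section 7 and section 8.6.2: treatment-emergent means onset from first dose through the follow-up visit, at latest Day 18. Tying the end to the visit, and not to a day count, also covers a late Visit 3.

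If the sponsor prefers a 7-day window, state it by onset in both sections and add a row or listing, by arm, of AEs with later onset through Visit 4.

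The cost is wording in two sections and, under the second option, one extra row or listing from data already collected. No visit, sample or staff is added. The downside of the first option is 1 to 4 extra off-drug days for a completer, which will bring in some background AEs. These are expected equally across the three blinded arms. Graded liver-test counts and a listing of special-interest events would be reasonable optional additions to the SAP.

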8.6.3 Clinical Laboratory Tests

For clinical laboratory data, mean changes from pre-treatment to post-treatment visits will be summarized using descriptive statistics. Cross-tabulations analysis will be performed for laboratory parameters with reference normal ranges. The laboratory data will be categorized as low, within, and above the reference normal ranges. The summary tables will tabulate the number and percentage of subjects with pre-treatment values below/within/above the normal reference range versus minimum/maximum/final post-treatment values below/within/above the normal reference range. Normal reference ranges will also be provided in the summary display. Laboratory parameters that are not specified in the protocol will not be included in the analysis.

8.6.4 Physical Examinations

Subjects with a physical examination performed at the Screening, Randomization, EOT, and Follow-up Visits will be displayed in a subject listing.

8.6.5 Vital Signs

Descriptive statistics will be provided to evaluate the absolute values and changes from baseline for any vital signs (blood pressure, heart rate, respiratory rate, temperature, and weight) measured during the study.

8.7 Data Quality Assurance

Steps to be taken to assure the accuracy and reliability of data include the selection of qualified Investigators and appropriate study sites, review of protocol procedures with the Investigator and associated personnel prior to the study, and periodic monitoring visits by the Sponsor or designee. Compliance will be achieved through a combination of study specific audits of investigational sites and audits at regular intervals of the Sponsor's systems for data handling, analysis, and reporting. eCRFs will be reviewed for accuracy and completeness by the Sponsor or designee during on-site monitoring visits and any discrepancies will be resolved with the Investigator or designees, as appropriate. The data will be entered into the clinical study database and verified for accuracy.

This study will be organised, performed, and reported in compliance with the Sponsor's Standard Operating Procedures, protocols and working practice documents, and the requirements of national and international GCP guidelines.

8.8 Data Collection

Original source data will be collected via source documents. Final data for this study will be collected using eCRFs. Data must be entered on to the eCRFs in English. All eCRFs must be completed in a timely manner before the Sponsor or designee performs a monitoring visit. The Principal Investigator will be required to electronically sign the eCRFs casebook for each subject. Laboratory reports must be reviewed, signed, and dated by an appropriate Investigator and filed with the source documents. Any laboratory findings out of the normal range should indicate the clinical significance (clinically significant [CS] or not-clinically significant [NCS]) of the results on both the source document and the corresponding eCRF.

The eCRFs are to be completed as soon as possible from the time of the subject's visit, with the exception of results of tests performed outside the Investigator's office, so that they always reflect the latest observations on the subjects participating in the study.

All eCRF corrections are to be made or reviewed by the Investigator or other authorized study site personnel.

Automatically generated queries will be answered by site personnel during the eCRF completion process.

The dates of the monitoring visits will be recorded by the monitor in a study site visit log to be kept at the site. The first post-initiation monitoring visit will usually be made as soon as possible after enrolment has begun. At these visits, the monitor will compare the data entered into the eCRFs with the hospital or clinic records (source documents). Source documentation must be available to substantiate proper informed consent procedures, adherence to protocol procedures, adequate reporting and follow-up of AEs, administration of concomitant

medication, medication receipt/dispensing/return records, and study medication administration information. Specific items required as source documents will be reviewed with the Investigator prior to the study. Findings from this review of eCRFs and source documents will be discussed with the Investigator. The Sponsor expects that, during monitoring visits, the Investigator and study coordinator, will be available, the original source documentation, regardless of media, will be available, and a suitable environment will be provided for review of study-related documents.

Draft

9. SPONSOR'S AND INVESTIGATOR'S RESPONSIBILITIES

This study will be conducted in accordance with current applicable regulations, ICH, and local ethical and legal requirements.

